6.5.2 USPE Product Evaluation: Web-based survey

Web-based surveys (~30-45 minutes) will include USPE items and scales, conventional acceptability questions, and behavioral and psychosocial measures capturing participant experiences during RAI/VI (e.g., partner type; sexual behavior; product use self-efficacy; willingness-to-use product). Additionally, participants will be asked open ended questions about what they liked/didn't like about the product, and any other recommendations that they might have. These answers may be used to remind participants of salient experiences to be discussed further during the in-depth interview (IDI, see section 6.4). After completing the sex-associated web-based survey, participants will be prompted to schedule their next study visit. Following completion of the final questionnaire, participants will complete a face-to-face qualitative in-depth interview (IDI), with survey item evaluation elements as applicable.³² The IDI will focus on a discussion of the participant's use experience and the factors that impacted that experience, including product factors and the interaction of product experience factors and other use factors (timing of application, sexual behavior sequencing, etc). Data will be collected regarding participants' experiences of each of the salient dimensions of sensory perceptions and product characteristics. The web-based survey will include scales adapted to capture the RAI and VI experiences using suppository formulations. In addition, the web-based survey will include other items relevant to sexual behavior and prevention, such as partner perception items. The survey system presents each item and its potential responses as a separate screen. USPE items are divided into two sections: insertion/application experience and RAI/VI experience (as applicable). Remaining items are positioned before and after USPE sections, as applicable.

The Perceptibility scales administered to participants in this study consist of statements (i.e., items), written in a factual tone, to which participants respond with varying levels of agreement (i.e., 1=Do Not Agree at All; 2=Agree a Little; 3=Agree Somewhat; 4=Agree a Lot; 5=Agree Completely). Scales are used frequently in psychological and social sciences to quantify experiences across participants, and to predict specific outcomes. Each item is designed to capture a specific construct, concept, or experience targeted in the study. In scale development, several items represent similar experiences, and can appear redundant to a participant (participants are instructed to read each item as a stand-alone experience and respond as such). These seemingly redundant items (i.e., as seen at face value) may actually be capturing underlying latent constructs that differ from each other. Scales often represent underlying constructs that are not necessarily identifiable at face value. Until the psychometric analyses are complete, the generation and evaluation of redundant items is critical to the development of reliable and valid scales. Ultimately,

with careful psychometric and conceptual analyses, scales will be finalized that lack redundancy and that capture experiences that are either mutually exclusive or that correlate with each other in consistent ways, but are not overlapping.

Each scale has a different number of items, and, therefore, a different potential score range. In interpreting each scale score, averaged item means will be considered as an indication of the overall disagreement-agreement for each scale. Thus, the item mean represents the general level of agreement the sample endorsed with respect to a given formulation experience. Female vaginal scales (from which the rectal scales were derived) were psychometrically validated in the Microbicide Innovation Program studies (MH080591),²³ as well as another MIP award (R33AI076967), and preliminary analyses of the adapted rectal scales from Project 5.1 (evaluating gel/cream formulations) and Project 4 (volume comparison imaging study) have been completed (see §1.1.1. *The Current IPCP's Progress in Rectal and Dual Compartment Perceptibility*). Comprehensive psychometric validation of the rectally-adapted scales cannot be accomplished until larger data sets can be accumulated: the DRUM-S data will be included in future validation analyses.

Scale items are organized within the questionnaire by the logical progression of activities in which a participant engages, or in which s/he experiences the products and study activities. The USPE scales used in this study fall into two broad categories, each of which is associated with a different product evaluation experience. The categories, as well as descriptive titles of the scales within each category, are as follows:

Application (Insertion) / Ambulation: Descriptive titles of the scales pertaining to the Application and Ambulation experience of participants are: Application Leakage; Application Ease; Application Discreet-Portable; Application Product Awareness; Application Lack of Awareness; Ambulation Product Movement; Ambulation Leakage; Ambulation Hygiene; Ambulation Stickiness; Ambulation Awareness; Ambulation Spreading Behavior²³

Sexual Activity: Descriptive titles of the scales pertaining to sexual activity are: Sex: Initial Penetration; Sex: Initial Lubrication; Sex: Spreading Behavior; Sex: Product Awareness; Sex: Perceived Wetness; Sex: Stimulating; Sex: Messiness; and Sex: Leakage.²³ Additional scales are being preliminarily validated in another of the IoR's studies, and will be evaluated here, as well. They include: Sex: Naturalness; Sex: Lubricity; Sex: Effortful; Sex: Pleasure; Sex: Precoital Leakage; and Sex: Noticeable

As part of their final web-based USPE survey after evaluating all three study products, participants will complete a final acceptability survey. This survey will focus on participants' preferences for study products, and will capture both a ranking of the study products and a forced choice. This approach will allow more nuanced comparisons across products and indications of willingness-to-use associated with each product.

In addition to the scales enumerated here, the overall measurement development activities include additional items that, alone (i.e., not as scale items), have shown significant differences in user experiences between vaginal gels with varying physicochemical and rheological properties. These items are also part of the current study's survey. It is hypothesized that these items capture unique constructs not fully captured within the parameter space of earlier studies and that they will either do so again, or, as a function of the current study's dosage form properties and the RAI/VI experience, begin to correlate and form new scales.

6.5.3 Qualitative In-Depth Interview Agenda

Questions for the IDI agendas have been derived from 1) extensive review of the formulation acceptability literature, 2) investigators' prior experience with user perceptibility studies and hypothesized correspondence with biophysical properties and functionality, and 3) the accumulation of knowledge

gained from our ongoing formulation perceptibility studies (including Project DRUM/5.1 and Project 4). Questions and probes are structured accordingly. A semi-structured qualitative agenda ensures that facilitators gather data across the same dimensions regarding biophysical properties and rheological performance of the dosage forms and their potential correspondence to user perceptions. The agenda is written to assist the facilitator but is not a rigid script that must be adhered to. This ensures that each facilitator gathers data on the same topics, but affords flexibility of natural narrative conversation to pursue a priori topics, as well as emergent themes as encountered.

The agenda includes discussion of the participant's perceptions of the products, while gathering data on the language s/he uses to describe it. Lines of inquiry will include participant perceptions and thoughts regarding the applicable salient dimensions of sensory perceptions and product characteristics: experiences of leakage (or dryness), for example, and what degree of leakage (or dryness) is tolerable versus not; how use of each formulation influences sexual pleasure and/or comfort during sex; perceptions of ease of insertion, dosage form volume considerations, and implications for covert use when using each dosage form. Participants will be asked to: a) discuss any steps they take to prepare for anal or vaginal intercourse (e.g., douching, enema, lubricant use), b) discuss their perceptions of the product insertion process, including its ease or difficulty, b) describe if, when, and under what conditions each product leaked out of the rectum/vagina, c) describe awareness of the product during RAI/VI, including perceptions of presence/absence, moisture, wetness, dryness, etc., d) discuss product behavior as it impacts the experience of sex, including lubrication or desiccating properties, perceptions of interference, sexual pleasure and/or comfort, etc., including the product's impact on use of sex toys, if applicable; e) consider whether the products might be used covertly, and f) discuss volume considerations in the context of RAI. Throughout, the participants will be asked to assess both positive and negative aspects of product characteristics and behavior. The goal is to establish an understanding of the potential correspondence between product properties and functionality, users' perceptions of the behavioral dimensions of interest (listed above) and to assess if any new experiences or domains exist for suppository formulations. For female participants, an additional line of inquiry will be to discuss how RAI is perceived in context overall, and how using such a product for RAI, VI, or dual compartment protection may impact sexual sequencing and her overall sexual experiences. Participants' assumptions or opinions about how their sexual partners may have experienced the products will be an element of the discussion, if appropriate.

As IDIs are completed, the research team will review constructs/concepts addressed and the language participants use to describe their sensory perceptions and experiences. These constructs/concepts and language will be used to further adapt existing items as necessary and generate new items unique to the suppository use experience and the interplay between RAI and vaginal sex (for female participants).

Study Completion Debriefing

At the end of the final visit (Visit 5), after all study-related activities have been completed, each participant will be debriefed by study staff. The debriefing will consist of thanking them for their time and effort in completing the study, and reminding them of the study purpose. In particular, the study staff will remind the participants of the challenge of developing effective HIV prevention products and that it is critical that a product be safe, effective, and acceptable. An acceptable product is one that will be used correctly and consistently (i.e., adherence); thus it is important that it have a neutral impact on the sexual experience, increase comfort/pleasure during RAI/VI or, at a minimum, not increase discomfort. Their efforts in this study will help scientists design a (dual compartment) microbicide that elicits these USPEs, so that the goal of reducing the HIV/AIDS pandemic can be realized.

7. Safety

7.1 Clinical Management of Adverse Events

7.1.1. General Adverse Events

By definition, an adverse event can be either a new finding or symptom, or a worsening of a pre-existing condition. In order to accurately capture adverse events in follow-up, all volunteers will be clinically screened, and a medical history obtained by the study clinician at V1, before enrollment in the product evaluation portion of the study. Adverse events (e.g., fever, pain) will be elicited during the daily phone survey and during study visits. Referral to appropriate care will be offered to participants as needed. Criteria for product hold for AEs, and for discontinuation of an individual's participation in the study are described below.

While the two OTC study products and the HEC placebo gel are overall considered safe, side effects or adverse events are possible and could occur in the context of any of the three product evaluations. Self-administration of study product could result in trauma to the anus, rectum, vagina, or genitals. In addition, side effects, including itching, burning, redness, rash or hives, are possible with any rectal or vaginal product use. Participants might also experience pain and/or discomfort during RAI/VI itself.

Should an adverse event or side effect be reported, study staff will first collect relevant information and contact the study clinician to determine whether the participant will be seen immediately or referred to her/his personal physician. If the event does not require immediate triage or treatment, study staff (or the study clinician) will discuss a plan, or any alternative referrals, and, if applicable, request that s/he sign a Release of Information form so that study staff can follow up on the event through resolution. Study staff will complete a follow-up phone call with the participant within 72 hours, to determine whether the event has been resolved, whether treatment was sought, what treatment was provided, and any other information that would 1) assure the participant has been properly treated, and 2) help to categorize the event for AE reporting purposes. Staff will continue to follow up with the participant until adequate resolution can be verified. If staff or the participant finds it necessary, referral back to the study clinician will be made promptly.

7.1.2 Pregnancy

Pregnancy during study participation is unlikely due to the requirement for effective contraception. However, urine pregnancy tests will be performed during each study visit for all female participants.

If a female participant has a positive pregnancy test, she will be referred via the study's clinician to appropriate care of her choice, inside or outside the Miriam Hospital/Lifespan network.

7.1.3 HIV Infection

HIV testing is scheduled at the Screening Visit. HIV pre- and post-test counseling will be conducted by clinical staff, or non-clinical research staff trained in HIV/STI/hepatitis counseling and testing by the Rhode Island Department of Health. Research staff conducting rapid HIV counseling and testing will communicate non-reactive results to participants as well as the study clinician. If a participant's result is reactive, he or she will be referred to the study clinician for follow-up confirmatory testing and referrals as appropriate. If a participant's result is invalid, study staff will run a second rapid test. The State of Rhode Island Department of Health (RIDOH) requires the reporting of positive test results for: Neisseria gonorrhoea, chlamydia trachomatis and syphilis within 4 days of diagnosis and HIV/AIDS within 14 days of diagnosis.

7.1.4 Criteria for Discontinuation

Participants may voluntarily withdraw from the study for any reason at any time. The Site PI/designee or study clinicians also may withdraw participants from the study to protect their safety and/or if they are unwilling or unable to comply with required study procedures. Participants also may be withdrawn if the study sponsors, government or regulatory authorities, including the Office of Human Research Protections (OHRP), or site IRBs terminate the study prior to its planned end date. Every reasonable effort will be made to complete a final evaluation of participants who withdraw or are withdrawn from the study prior to completing Visit 5. Study staff members will record the reason(s) for all withdrawals in participants' study records.

Product Hold

Product holds are not anticipated as this study involves single exposures to each of the three study products, none of which contain anti-HIV agents. If a Grade 2 or higher AE occurs, the PSRT will meet to discuss participant care/referral, any additional product or procedure revisions/resolutions, and to determine study status overall should the event be deemed related to product use.

Permanent Study Product Evaluation Discontinuation

The criteria for permanent discontinuation of further study product evaluations for an individual participant are:

1. Pregnancy
2. Request by participant to terminate study product
3. Clinical condition(s), which in the best judgment of the study clinician, are believed to be harmful or potentially life-threatening to the participant, even if not addressed in the AE management section of the protocol
4. Recommendation by the IRB, PSRT, DAIDS Medical Officer, OHRP, or FDA

The participant will continue to be followed with his/her permission if study product is discontinued. No subsequent modifications to the visit schedule and duration of continued follow-up will be made, except for discontinuation of the study product. Any participant withdrawn due to pregnancy will be followed for pregnancy outcomes, with her permission.

Participants who have not engaged in RAI/VI with study products and completed a web-based survey (i.e., product evaluation activities) after ~10 days will be contacted by the study team to ensure that they understand the study requirements and are still willing and able to comply. If a participant still has not completed product evaluation activities after ~20 days, they will be contacted again by the study team to again discuss whether they are willing and able to continue participating in the study. If a participant has not completed a product evaluation web-based survey after ~28 days, they may be withdrawn from the study (at the discretion of the PI or designee, depending on the individual circumstances of the participant). Participants who voluntarily withdraw from the study or who are withdrawn for safety or protocol compliance reasons will be replaced, if the study timeline allows. That is, given study timeline availability, additional participants will be enrolled to reach approximately 20-30 completed participants.

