Study Design	Single-site, pre-phase 1, mixed methods USPE instrument development study
Study Population	Healthy, HIV uninfected participants, male ≥ 18 years of age and female 18-45 years of age. By history receptive anal intercourse (RAI) at least twice in the past 6 months and women in addition vaginal-penile intercourse (VI) at least twice in the past 6 months.
Sample Size	Approximately 20-30 participants (~10-15 males; ~10-15 females). Our goal is to recruit a minimum of ~7-10 males and ~7-10 females. Ranges are provided to allow for a gender imbalance in the sample if we experience difficulty with recruitment, and to allow for achieving data saturation in qualitative data collection.
Study Contacts	
Visit 0: Pre-screening (by phone or in person) to confirm basic eligibility
 
Visit 1: Informed consent (Screening), STI/HIV screening; pregnancy screening (females); CASI Clinic Survey
 
Visit 2: Pregnancy screening (females), informed consent (Formulation Evaluation), random assignment to order of study products, provision of 1st study product, CASI Baseline Survey
 
Visits 3-4: Pregnancy screening (females), provision of 2nd and 3rd study products, respectively
 
Visit 5: In-depth qualitative interview (IDI) with survey evaluation (cognitive) elements
 
Visit 2-Visit 5: Automated daily phone check-ins Web-based USPE surveys completed following each occurrence of RAI/VI in conjunction with study product use. Final product acceptability survey completed after the final USPE survey. Compensation for all study activities completed since the previous visit (daily phone check-ins, web-based surveys) and not yet compensated, will occur with each study visit

Study Duration	
Study duration: Participant recruitment, enrollment, visit completions: 9-12 months. Analyses: within 24 months from start of study.
 
Per participant: Approximately 10-20 weeks. We do not anticipate the necessity of additional time beyond the range allotted for female participants to evaluate suppositories in both compartments (§3).

Study Regimen/ Intervention	
Products :
 
 -- HEC gel (CONRAD, Arlington, VA) – applicator insertion -- Key-E suppository –manual insertion -- Zetpil suppository – manual insertion

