2.1.2 Exploratory Endpoints

- (3) Collect participant-reported information regarding the safety of the suppository forms. The information collected will include any adverse events (and their severity grading) deemed to be related to the dosage form by the study clinical staff and/or in consultation with the DAIDS Medical Officer. Frequency of specific related adverse events (and their severity) will be calculated cumulatively.

(4) Identify formulation-specific classes of USPE scale scores (Sex-associated scales): by sex (males, females), by compartment (Rectum: males and females. Vagina: females), resulting from Latent Class modeling analyses, given adequate final evaluable sample sizes.

3. Study Design

Visits occur at study clinic (V1) or behavioral lab (V2-V5). Product evaluation activities (RAI (receptive anal intercourse); VI (vaginal intercourse)) represented by triangles occur outside the clinic (e.g., participant's home). ALL participants complete study product evaluations with RAI. FEMALE participants also complete study product evaluations with VI.

This study is a single-site pre-Phase 1 USPE measure development study, utilizing a formative mixed-method design (i.e., incorporating qualitative and quantitative data collection methods). Approximately 20-30 participants (~10-15 males and ~10-15 females) will evaluate three products (Key-E®, Zetpil®, and HEC gel), on separate occasions, during RAI. In addition, female participants will evaluate the suppository products during vaginal sex. Participants will be assigned to one of six possible product orders.

Female participants are not required to have RAI and VI in the same sexual episode, or in different sexual episodes: we will allow them to choose, so that we can begin to understand how sexual sequencing may/may not play a role in product use for women. All participants will be instructed verbally and in writing to limit suppository use to a total of 2 per day, for the women, regardless of rectal or vaginal use.

Participant recruitment, enrollment, and visit completions will require approximately 9-12 months. Analyses (both quantitative and qualitative) will be complete within 24 months from study initiation. Results, in the form of USPE scale scores, by product, sex, and compartment, will be computed. Preliminary psychometric analyses of scales will be completed, given adequate evaluable sample size.

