4.2 Inclusion Criteria

All participants must meet all of the inclusion criteria to participate in this study.

- Eligible male participants must be 18 years of age or older
- Eligible female participants must be 18-45 years of age
- Report receptive anal intercourse (RAI) at least twice in the past 6 months,
- Are willing to use each study product in conjunction with RAI on at least one occasion in each data collection period (resulting in a minimum of 3 RAI events during the study)
- Are willing and able to respond to study data collection systems via phone and internet, attend all study visits, and participate in in-depth qualitative interviews

Additional Inclusion Criteria for Female Volunteers:

- report vaginal-penile intercourse (VI) at least twice in the past 6 months,
- willing to use each study suppository formulation in conjunction with VI on at least one occasion in each data collection period (resulting in a minimum of 2 vaginal intercourse events during the course of the study)
- report consistent use of an effective birth control method: e.g., hormonal contraceptive, IUD, bilateral tubal ligation, Essure® or any non-incisional permanent birth control procedure, hysterectomy (partial or total, with/without oophorectomy), partner's vasectomy/salpingectomy

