6.4.4 Product Provision

Following the demonstration(s), study staff will review the study procedures and guidelines with the participant and then provide the participant with two (2) doses of their assigned study product, and written instructions for inserting the product and using the condoms: the 2nd dose is provided only as a back-up, in case the 1st dose is dropped or sex does not occur after product insertion. All participants (male and female) will be instructed to use the study product during RAI at least once during the product evaluation period (~2 weeks). Female participants will also be instructed to use a separate dose of the suppository products for VI. When suppository products are provided, participants will be instructed to wait 15 minutes before rectal or vaginal intercourse to allow for product dissolution. Participants will be strongly encouraged to use condoms throughout the duration of the study (§4.5).

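### Section 7.1.4 does not expect product holds because exposures are single, but women are planned to use each suppository at least twice, and the protocol body sets no default pause on doses at home after a Grade 2+ AE

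*Combined protocol and SAP*

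**What the plan says.** Section 7.1.1 points forward to hold rules: "Criteria for product hold for AEs, and for discontinuation of an individual's participation in the study are described below". The only text that answers it is the Product Hold paragraph of 7.1.4. That paragraph opens with "Product holds are not anticipated as this study involves single exposures to each of the three study products, none of which contain anti-HIV agents" and continues: "If a Grade 2 or higher AE occurs, the PSRT will meet to discuss participant care/referral". The rest of that sentence adds possible changes to product or procedures, and the status of the study if the event is judged product-related. It gives no deadline for the meeting and no instruction about product use in the meantime.

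On exposure, section 4.2 requires every participant to be willing to use each product at least once with RAI. Women must also be willing to use each suppository with VI in its period, "resulting in a minimum of 2 vaginal intercourse events during the course of the study". Section 6.4.4 adds: "Female participants will also be instructed to use a separate dose of the suppository products for VI". The Study Duration entry of the Protocol Summary likewise allows time "for female participants to evaluate suppositories in both compartments". Section 3 leaves the sequence to the woman: "Female participants are not required to have RAI and VI in the same sexual episode, or in different sexual episodes".

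On supply, 6.4.4 hands over two doses at the start of each period of about two weeks and says "the 2nd dose is provided only as a back-up, in case the 1st dose is dropped or sex does not occur after product insertion".

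**The concern.** A reason given for not expecting holds is that each participant meets each product once. If that were so, an AE would normally follow the only use, and little would be left to hold within the period. For women and the suppositories it is not so: after the first use a second planned use of the same product may still be outstanding, and at least one dose may be at home. The standing instruction is to complete that second use.

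At stake is participant safety in the interval between reporting a Grade 2 or higher AE and a decision on product. Changing compartment does not avoid re-exposure for the systemic Zetpil symptoms listed in 10.5.1, such as tremor, nausea and sleeplessness. The forward reference in 7.1.1 also leads site staff to look for hold criteria that are barely there.

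**Working it through.** **1. Planned minimum uses (sections 4.2 and 6.4.4).**

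| Product | Men | Women |
|---|---|---|
| HEC gel | 1 (RAI) | 1 (RAI) |
| Key-E | 1 (RAI) | 2 (RAI + VI) |
| Zetpil | 1 (RAI) | 2 (RAI + VI) |
| Total | 3 | 1 + 2 + 2 = 5 |

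Section 7.1.4 implies 3 for everyone. All these figures are minima, because 4.2 and 6.4.4 speak of at least one occasion. With about 10 to 15 women, planned repeat uses of the same suppository number at least 2 × 10 = 20 to 2 × 15 = 30. That counts planned repeats, not uses affected by an AE.

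**2. Men and the gel.** One purpose of the back-up dose is to cover an insertion not followed by sex. Using it then is a second exposure, for either sex and for any product.

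**3. Could single mean one per compartment?** Section 7.1.4 does not say so. Section 3 caps women at two suppositories a day counted across rectum and vagina together, so the protocol itself adds exposure over compartments.

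**4. Provisions that might pause the second use.**

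- 7.1.1: daily elicitation, clinician contact and a follow-up call within 72 hours. These cover triage and follow-up.
- 7.4.3: report to the DAIDS Medical Officer within 24 hours. This is reporting.
- 7.4.1, item 6: the AE record states the action taken on product. It records an action but does not prescribe one.
- 7.3: the Protocol Safety Review Team (PSRT) can meet urgently. No interim rule is given.
- 7.1.4: withdrawal or permanent discontinuation by judgement, request or recommendation. These are discretionary, and none is a temporary pause.
- 1.3.3: dispensing needs the clinician's prescription. This does not reach doses already at home.
- 4.4: an automatic hold on provision pending discussion, but only for use of prohibited products.
- 11.5: an AE-driven hold, but on enrollment.

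None sets a default for a dose at home until someone decides.

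**5. Is there an interval in which a pause could act?** Only when RAI and VI fall in different episodes. Allergic or sensitivity symptoms typically appear 12 to 36 hours after exposure (10.5.1) and phone surveys are daily (6.5.1), so an AE can be reported between two uses in a two-week period. A repeat in the same episode cannot be intercepted.

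**6. Why no count of affected uses is given.** The documents give neither an AE rate nor the share of women who separate the two acts. An illustration shows the spread. Let affected uses = 2 × N × p × s × w, where N is the number of women, p the assumed chance of a Grade 2+ AE not clearly unrelated after a first suppository use, s the assumed share of separate episodes, and w the chance that the gap exceeds g hours. If the two use times are independent and uniform over 336 hours, w = (1 − g/336)².

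- Low: g = 60 (36 + 24), w = 0.675; 2 × 10 × 0.01 × 0.25 × 0.675 = 0.03
- Middle: g = 36, w = 0.797; 2 × 12.5 × 0.05 × 0.5 × 0.797 = 0.50
- High: g = 12, w = 0.930; 2 × 15 × 0.10 × 1 × 0.930 = 2.8

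The range spans about 80-fold and rests wholly on assumed p, s and timing. It also has no term for a participant who declines the next dose or a clinician who advises against it. It therefore counts uses that a rule could intercept, not uses that would otherwise occur, and no conclusion here depends on it.

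**The case against.** The strongest reply is that the person who matters is already engaged. Staff must contact the study clinician when an AE is reported (7.1.1), and the clinician or designee grades severity and assigns relatedness (7.4.1). An event is known to be Grade 2 or higher and possibly related only once someone who can stop product has looked at it. The Medical Officer is told within 24 hours, sits on the PSRT (7.2), and can trigger permanent discontinuation by recommendation (7.1.4). This stands: a new sentence would add a default, not a missing power.

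It also stands that 7.1.4 is thin rather than empty, since it names a grade threshold and a responsible body, and that its second reason, the absence of anti-HIV agents, is not disputed. Two suppositories a day is within the dosing stated in 1.3.1 for both products, and the gel is a placebo.

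A reader might infer that the protocol has no means of stopping product after an AE, or that no stop-use advice exists anywhere. The documents do not support either. The first is contradicted by the provisions above. The second cannot be checked, because the consent forms, insertion instructions, phone-survey flow chart and operations manual are not in the supplied text and are natural places for such advice.

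What the reply does not rescue is the exposure statement, or the absence from the protocol body of an instruction covering the time before a decision.

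**Conclusion.** The premise in 7.1.4 is wrong as written: women have at least two planned uses of each suppository, and a back-up dose can repeat exposure for anyone. The hold criteria promised in 7.1.1 amount to a PSRT meeting with no deadline and no default pause. Discretionary authority to stop limits the consequence, expected harm is low, and the number of uses affected cannot be computed from the documents.

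This rests on the supplied protocol body alone. Doses left after a first use are also uncertain. It is one if women receive the two doses in 6.4.4, but 1.3.1 describes two doses per evaluation, and neither section says whether women receive more to cover VI. Severity is minor: a factual correction with a cheap safety improvement attached.

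**What to change.** In the Product Hold paragraph of 7.1.4:

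1. Replace the clause about single exposures with: *at least one planned use of each product for men and, for women, at least one use of the gel and at least two of each suppository (rectal and vaginal)*.
2. Add: *If a Grade 2 or higher AE that is not clearly unrelated to study product is reported, the participant will be told to use no further dose, and none will be dispensed, until the study clinician (with the PSRT as already required) documents a decision to resume, skip that product or discontinue.*

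Record the decision under item 6 of the AE description in 7.4.1. Section 4.4 already has a comparable pause for prohibited products, so the form is familiar to the site.

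The cost is two short edits that use the existing AE record and PSRT meeting. Some evaluations will be delayed, and an occasional within-woman comparison of RAI with VI for a suppository may be lost. That is tolerable in a formative study where, by 8.3.1, standard hypothesis testing is not an endpoint.
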